2.2 Violations and deviations

The following general categories will be considered important protocol deviations and will be raised in the Clinical Trial Management System (CTMS) log.. These will be listed and discussed in the clinical study report (CSR) as appropriate:

Dose-finding phase

- Deviation 1: Patients who received a dose of study treatment other than the dose that was intended
 - 1.1 Patient either did not receive any dose of planned study treatment or did not receive the correct dose of planned study treatment (i.e. less than 75% of the planned dose at the time of infusion) (as per Figure 1 in the CSP).
- Deviation 2: Patients who deviate from key entry criteria as per the CSP. These are inclusion criteria 2, 3, and 8 and exclusion criteria 2, 3, 5, 6, 7 and 11:
 - 2.1 Patient, older than 18 years, received study treatment (inclusion criteria 2)

- 2.2 Patient received study treatment without a histopathologic confirmation of a malignancy or/and have not progressed or were refractory to standard therapies or/and have not explored standard of care treatments before participation on this protocol. (inclusion criteria 3)
- 2.3 Patient with a hematological condition listed in the protocol received treatment
- 2.4 Inadequate organ and marrow function, defined as any of the following (inclusion criteria 8):
- Hemoglobin < 9.0 g/dL
 - Absolute neutrophil count < $1.0 \times 10^9/L$
 - Platelet count < $75 \times 10^9/L$
 - Serum bilirubin > $1.5 \times$ the ULN
 - Creatinine clearance ≤ 60 mL/min
 - Alanine transaminase (ALT) or aspartate transaminase (AST) > $3 \times$ upper limit of normal (ULN) (for patients without liver metastases)
 - ALT or AST > $5 \times$ ULN (for patients with liver metastases)
- 2.5 Patients with a history of primary immunodeficiency an uncontrolled intercurrent illness that would limit compliance with study requirements, substantially increase risk of incurring AEs from IP, or compromise the ability of the patient to give written informed consent received study treatment.
- 2.6 Patients with unresolved toxicities with a severity of grade ≥ 2 (as determined by NCI CTCAE version 5.0) from previous anticancer therapy (excluding alopecia, vitiligo, lymphopenia, the laboratory values defined in the inclusion criteria and toxicities not reasonably expected to be exacerbated by treatment with durvalumab or tremelimumab) received study treatment. (excluding criteria 6).
- 2.7 Patients with known or clinically suspected active brain metastases or spinal cord compression that have not been treated or/and were considered unstable or/and were dependent on steroids above physiologic replacement dose, received study treatment (exclusion criteria 7).
- 2.8 Hypothyroidism before the start of treatment and worsening at any stage before the start of cycle 3. (inclusion criteria 2)
- 2.9 Received the last dose of an anticancer therapy (chemotherapy, immunotherapy, endocrine therapy, targeted therapy, biologic therapy, tumor embolization, or

mAbs) ≤ 28 days or less than 5 half-lives of the drug, whichever is shorter (and minimum of 7 days), prior to the first dose of study treatment (exclusion criteria 11).

2.10 Received any anti-cancer therapy (chemotherapy, immunotherapy, endocrine therapy, targeted therapy, biologic therapy, tumor embolization, or mAbs) between Cycle 1, Day 1 and Cycle 3, Day 1 (exclusion criteria 11).

Patient was dosed with study treatment, but fulfilled any of the following criteria:

2.11 Have or have had documented autoimmune or inflammatory disorders (exclusion criteria 2) excluding:

- Patients with hypothyroidism not controlled by endocrine therapy, where 'controlled' is defined as having a thyroid stimulating hormone (TSH) measurement within normal range at baseline
- Known psoriasis that requires systemic therapy
- Celiac disease, not controlled by diet alone.

2.12 Have an active infection (exclusion criteria 3).

2.13 Have tuberculosis (defined by clinical diagnosis or radiographic findings and/or a positive skin test), hepatitis B (defined by a positive surface antigen result), active hepatitis C (defined by a positive polymerase chain reaction (PCR) for hepatitis C virus (HCV) ribonucleic acid (RNA)) or human immunodeficiency virus (HIV) (defined as positive HIV 1/2 antibodies) (exclusion criteria 5).

- Deviation 3: Received prohibited concomitant medications (including other anticancer agents). Please refer to the CSP section 6.4 for those medications that are detailed as being 'excluded' from permitted use during the study. This will be used as a guiding principle for the physician review of all medications prior to database lock to identify those likely have an impact on efficacy.

3.1 Prior treatment with immune-mediated therapy of any of the following

- Anti-PD-L1
- Anti-PD-1
- Anti- Programmed cell death ligand 2(PD-L2)
- Anti- Cytotoxic T-lymphocyte-associated antigen 4 (CTLA-4)
- Antibodies of chimeric antigen receptor T-cell therapy (CAR-T) or other cell therapies

3.2 Receive a live attenuated vaccine within 30 days prior to the first dose of study treatment

3.3 Receive an immunosuppressive medication within 14 days prior to the first dose of study excluding;

- Intranasal, inhaled, topical steroids, or local steroid injections (e.g. intra-articular injection).
- Systemic corticosteroids at physiologic doses as replacement therapy, not to exceed 10 mg/m²/day of prednisone or its equivalent.
- Steroids as premedication for hypersensitivity reactions (e.g. computed tomography (CT) scan premedication).

Dose-expansion phase

- Deviation 1: Patients who received a dose of study treatment other than the dose that was intended

1.1 Patient either did not receive any dose of planned study treatment or did not receive the correct dose of planned study treatment (i.e. less than 75% of the planned dose at the time of infusion) (as per Figure 1 in the CSP).

- Deviation 2: Patients who deviate from key entry criteria as per the CSP. These are inclusion criteria 2, 3, 6 and 8 and exclusion criteria 11:

- 2.1 Patient, older than 18 years, received study treatment (inclusion criteria 2).
- 2.2 Patient received study treatment without a histopathologic confirmation of a malignancy or/and have not progressed or were refractory to standard therapies or/and have not explored standard of care treatments before participation on this protocol. (inclusion criteria 3).
- 2.3 Selection of a previously radiated tumor as a target lesion and tumor did not show disease progression prior to study entry (inclusion criteria 6).
- 2.4 Inadequate organ and marrow function, defined as any of the following (inclusion criteria 8):
 - Hemoglobin < 9.0 g/dL
 - Absolute neutrophil count < $1.0 \times 10^9/L$
 - Platelet count < $75 \times 10^9/L$
 - Serum bilirubin > $1.5 \times$ the ULN

- Creatinine clearance ≤ 60 mL/min
 - Alanine transaminase (ALT) or aspartate transaminase (AST) $>3 \times$ upper limit of normal (ULN) (for patients without liver metastases)
 - ALT or AST $> 5 \times$ ULN (for patients with liver metastases)
- 2.5 Received the last dose of an anticancer therapy (chemotherapy, immunotherapy, endocrine therapy, targeted therapy, biologic therapy, tumor embolization, or mAbs) ≤ 28 days or less than 5 half-lives of the drug, whichever is shorter (and minimum of 7 days), prior to the first dose of study treatment (exclusion criteria 11).
- 2.6 Received any anti-cancer therapy (chemotherapy, immunotherapy, endocrine therapy, targeted therapy, biologic therapy, tumor embolization, or mAbs) between Cycle 1, Day 1 and Cycle 3, Day 1 (exclusion criteria 11).
- Deviation 3: Baseline assessment > 21 days before start date of first dose of study treatment.
 - Deviation 4: Received prohibited concomitant medications (including other anticancer agents). Please refer to the CSP section 6.4 for those medications that are detailed as being ‘excluded’ from permitted use during the study. This will be used as a guiding principle for the physician review of all medications prior to database lock to identify those likely have an impact on efficacy.
 - 4.1 Prior treatment with immune-mediated therapy of any of the following
 - Anti-PD-L1
 - Anti-PD-1
 - Anti- Programmed cell death ligand 2(PD-L2)
 - Anti- Cytotoxic T-lymphocyte-associated antigen 4 (CTLA-4)
 - Antibodies of chimeric antigen receptor T-cell therapy (CAR-T) or other cell therapies
 - Deviation 5: Had non-measurable disease at baseline
 - Deviation 6: Had a solitary measurable lesion that was biopsied prior to study entry
 - Deviation 7: Imaging modalities for imaging acquired at baseline and first subsequent scan were not consistent (e.g. bone scan used for baseline, followed by CT scan post baseline)

3 PRIMARY AND SECONDARY VARIABLES

3.1 Derivation of visit tumor responses

The analysis of the primary endpoint, ORR, and the analyses of the secondary endpoints, PFS, DoR, and DCR, will be based on the site Investigator assessments using the following criteria

Table 5 Criteria for Investigator assessments

Type of cancer	Criteria
Solid Tumors	
SARCOMA and STO	RECIST 1.1 (see CSP Appendix E)

All RECIST 1.1, whether scheduled or unscheduled, will be included in the calculations. This is also regardless of whether a patient discontinues study treatment or receives another anticancer therapy.

Baseline will be assessed within the 21 days prior to first dose of study treatment and ideally as close as possible to the start of study treatment. Assessments are performed every 8 weeks (relative to the date of first dose of study treatment) in the first instance. For patients who achieve an objective response or stable disease, and for whom the response is still evident at 12 months, subsequent tumor assessments are to occur every 16 weeks \pm 1 week until disease progression.

If an unscheduled assessment is performed, and the patient has not progressed, every attempt should be made to perform the subsequent assessments at their scheduled visits. This schedule is to be followed in order to minimise any unintentional bias caused by some patients being assessed at a different frequency than other patients.

3.1.1 Derivation of RECIST 1.1 visit responses

For all patients with solid tumors excluding NB (SARC-1, SARC-2 and STO (dose-finding), SARCOMA and STO (dose-expansion)), the RECIST tumor response data will be used to determine each patient's visit response according to RECIST 1.1. It will also be used to determine if and when a patient has progressed in accordance with RECIST 1.1 and their BoR to study treatment.

From the Investigator's review of the imaging scans, the RECIST tumor response data will be used to determine each patient's visit response according to RECIST 1.1. At each visit, patients will be programmatically assigned a RECIST 1.1 visit response of complete response (CR), partial response (PR), stable disease (SD), or PD, using the information from target

lesions (TLs), non-target lesions (NTLs) and new lesions and depending on the status of their disease compared with baseline and previous assessments. If a patient has had a tumor assessment that cannot be evaluated then the patient will be assigned a visit response of NE, (unless there is evidence of progression in which case the response will be assigned as PD).

RECIST outcomes (i.e. PFS, ORR etc.) will be calculated programmatically for the site Investigator data (see Section 3.2) from the overall visit responses.

3.1.1.1 Target lesions (TLs) – site Investigator data

Measurable disease is defined as having at least one measurable lesion, not previously irradiated, which is ≥ 10 mm in the longest diameter (LD), (except lymph nodes which must have short axis ≥ 15 mm) with CT or magnetic resonance imaging (MRI) and which is suitable for accurate repeated measurements. A patient can have a maximum of 5 measurable lesions recorded at baseline with a maximum of 2 lesions per organ (representative of all lesions involved and suitable for accurate repeated measurement) and these are referred to as TLs. If more than one baseline scan is recorded, then measurements from the one that is closest and prior to first dose will be used to define the baseline sum of TLs. It may be the case that, on occasion, the largest lesion does not lend itself to reproducible measurement. In which circumstance the next largest lesion, which can be measured reproducibly, should be selected.

All other lesions (or sites of disease) not recorded as TL should be identified as NTLs at baseline. Measurements are not required for these lesions, but their status should be followed at subsequent visits.

Note: For patients who do not have measurable disease at entry (i.e. no TLs) but have non-measurable disease, evaluation of overall visit responses will be based on the overall NTL assessment and the absence/presence of new lesions (see Section 3.1.1.3 for further details). If a patient does not have measurable disease at baseline, then the TL visit response will be not applicable (NA).

Table 6 TL Visit Responses (RECIST 1.1)

Visit Response	Description
CR	Disappearance of all TLs. Any pathological lymph nodes selected as TLs must have a reduction in short axis to <10 mm.
PR	At least a 30% decrease in the sum of diameters of TLs, taking as reference the baseline sum of diameters as long as criteria for PD are not met.
SD	Neither sufficient decrease in sum of diameters to qualify for PR nor sufficient increase to qualify for PD.
PD	A $\geq 20\%$ increase in the sum of diameters of TLs and an absolute increase of $\geq 5\text{mm}$, taking as reference the smallest previous sum of diameters since treatment started including the baseline sum of diameters.
NE	Only relevant if any of the TLs were not assessed or NE or had a lesion intervention at this visit. Note: If the sum of diameters meets the progressive disease criteria, progressive disease overrides NE as a TL response.
NA	No TLs are recorded at baseline.

CR Complete response; PD Progressive disease; PR Partial response; SD Stable disease; NA Not applicable; NE Not estimable.

Rounding of TL data

For calculation of PD and PR for TLs percentage changes from baseline and previous minimum should be rounded to one decimal place before assigning a TL response. For example, 19.95% should be rounded to 20.0% but 19.94% should be rounded to 19.9%.

Missing TL data

If all TL measurements are missing then the TL visit response is NE. Overall visit response will also be NE, unless there is a progression of non-TLs or new lesions, in which case the response will be PD.

Lymph nodes

For lymph nodes, if the size reduces to < 10 mm then these are considered non-pathological. However, a size will still be given, and this size should still be used to determine the TL visit response as normal. In the special case where all lymph nodes are < 10 mm and all other TLs

are 0mm then although the sum may be > 0 mm the calculation of TL response should be over-written as a CR.

TL visit responses subsequent to CR

A CR can only be followed by CR, PD or NE. If a CR has occurred, then the following rules at the subsequent visits must be applied:

- Step 1: If all lesions meet the CR criteria (i.e. 0mm or < 10 mm for lymph nodes) then response will be set to CR irrespective of whether the criteria for PD or TL is also met i.e. if a lymph node LD increases by 20% but remains < 10 mm.
- Step 2: If some lesion measurements are missing but all other lesions meet the CR criteria (i.e. 0mm or < 10 mm for lymph nodes) then response will be set to NE irrespective of whether, when referencing the sum of TL diameters, the criteria for PD are also met.
- Step 3: If not all lesions meet the CR criteria and the sum of lesions meets the criteria for PD then response will be set to PD.
- Step 4: If after steps 1 – 3 a response can still not be determined the response will be set to remain as CR.

TL too big to measure

If a TL becomes too big to measure this should be indicated in the database and a size ('x') above which it cannot be accurately measured should be recorded. If using a value of x in the calculation of TL response would not give an overall visit response of PD, then this will be flagged and reviewed by the study team blinded to treatment assignment. It is expected that a visit response of PD will remain in the vast majority of cases.

TL too small to measure

If a TL becomes too small to measure, then this will be indicated as such on the eCRF and a value of 5mm will be entered into the database and used in TL calculations. However, a smaller value may be used if the radiologist has not indicated 'too small to measure' on the eCRF and has entered a smaller value that can be reliably measured. If a TL response of PD results, then this will be reviewed by the study team.

Irradiated lesions/lesion intervention

Previously irradiated lesions (i.e. lesion irradiated prior to entry into the study) should be recorded as NTLs and should not form part of the TL assessment.

Any TL (including lymph nodes), which has had intervention during the study (for example, irradiation / palliative surgery / embolization), should be handled in the following way and

once a lesion has had intervention then it should be treated as having intervention for the remainder of the study noting that an intervention will most likely shrink the size of tumors:

- Step 1: the diameters of the TLs (including the lesions that have had intervention) will be summed and the calculation will be performed in the usual manner. If the visit response is PD, this will remain as a valid response category.
- Step 2: If there was no evidence of progression after step 1, treat the lesion diameter (for those lesions with intervention) as missing and if $\leq 1/3$ of the TLs have missing measurements then scale up as described in the 'Scaling' section below. If the scaling results in a visit response of PD then the patient would be assigned a TL response of PD.
- Step 3: If, after both steps, PD has not been assigned, then, if appropriate (i.e. if $\leq 1/3$ of the TLs have missing measurements), the scaled sum of diameters calculated in step 2 should be used, and PR or SD then assigned as the visit response. Patients with intervention are evaluable for CR as long as all non-intervened lesions are 0 (or $<10\text{mm}$ for lymph nodes) and the lesions that have been subject to intervention have a value of 0 (or $<10\text{mm}$ for lymph nodes) recorded. If scaling up is not appropriate due to too few non-missing measurements, then the visit response will be set as NE.

At subsequent visits, the above steps will be repeated to determine the TL and overall visit response. When calculating the previous minimum, lesions with intervention should be treated as missing and scaled up (as per step 2 above).

Scaling (applicable only for irradiated lesions/lesion intervention)

If $> 1/3$ of TL measurements are missing (because of intervention) then the TL response will be NE, unless the sum of diameters of non-missing TL would result in PD (i.e. if using a value of 0 for missing lesions, the sum of diameters has still increased by 20% or more compared to nadir and the sum of TLs has increased by $\geq 5\text{mm}$ from nadir).

If $\leq 1/3$ of the TL measurements are missing (because of intervention) then the results will be scaled up (based on the sizes at the nadir visit to give an estimated sum of diameters and this will be used in calculations; this is equivalent to comparing the visit sum of diameters of the non-missing lesions to the nadir sum of diameters excluding the lesions with missing measurements).

Example of scaling

Lesion	Longest diameter at nadir visit	Longest diameter at follow-up visit
1	7.2	7.1
2	6.7	6.4
3	4.3	4.0
4	8.6	8.5
5	2.5	Intervention
Sum	29.3	26

Lesion 5 is missing at the follow-up visit; there was a baseline TL sum of 29.3cm.

The sum of lesions 1-4 at the follow-up is 26 cm. The sum of the corresponding lesions at the nadir visit is 26.8 cm.

Scale up as follows to give an estimated TL sum of 28.4cm:

$$26/26.8 \times 29.3 = 28.4 \text{ cm}$$

CR will not be allowed as a TL response for visits where there is missing data. Only PR, SD or PD (or NE) could be assigned as the TL visit response in these cases. However, for visits with $\leq 1/3$ lesion assessments not recorded, the scaled-up sum of TLs diameters will be included when defining the nadir value for the assessment of progression.

Lesions that split in two

If a TL splits in two, then the LDs of the split lesions should be summed and reported as the LD for the lesion that split.

Lesions that merge

If two TLs merge, then the LD of the merged lesion should be recorded for one of the TL sizes and the other TL size should be recorded as 0cm.

Change in method of assessment of TLs

CT, MRI, and clinical examination are the only methods of assessment that can be used within a trial, with CT and MRI being the preferred methods and clinical examination only used in special cases. If a change in method of assessment occurs, between CT and MRI this will be considered acceptable and no adjustment within the programming is needed.

If a change in method involves clinical examination (e.g. CT changes to clinical examination or vice versa), any affected lesions should be treated as missing. The TL visit response may still be evaluable if the number of missing TL measurements at a visit is $\leq 1/3$ of the total number of TLs.

3.1.1.2 Non-target lesions (NTLs) and new lesions – site Investigator data.

At each visit, the Investigator should record an overall assessment of the NTL response. This section provides the definitions of the criteria used to determine and record overall response for NTL at the investigational site at each visit.

NTL response will be derived based on the Investigator’s overall assessment of NTLs as follows

Table 7 NTL Visit Responses (RECIST 1.1)

Visit Responses	Description
CR	Disappearance of all NTLs present at baseline with all lymph nodes non-pathological in size (<10 mm short axis).
PD	Unequivocal progression of existing NTLs. Unequivocal progression may be due to an important progression in one lesion only or in several lesions. In all cases, the progression MUST be clinically significant for the physician to consider changing (or stopping) therapy.
Non-CR/Non-PD	Persistence of one or more NTLs with no evidence of progression.
NE	Only relevant when one or some of the NTLs were not assessed and, in the Investigator's opinion, they are not able to provide an evaluable overall NTL assessment at this visit. Note: For patients without TLs at baseline, this is relevant if any of the NTLs were not assessed at this visit and the progression criteria have not been met.
NA	Only relevant if there are no NTLs at baseline.

CR Complete response; NTL Non-target lesion; PD Progressive disease; PR Partial response; SD Stable disease; TL Target lesions; NA Not applicable; NE Not estimable.

To achieve ‘unequivocal progression’ on the basis of NTLs, there must be an overall level of substantial worsening in non-target disease such that, even in the presence of SD or PR in TLs, the overall tumor burden has increased sufficiently to merit a determination of disease progression. A modest ‘increase’ in the size of one or more NTLs is usually not sufficient to qualify for unequivocal progression status.

Details of any new lesions will also be recorded with the date of assessment. The presence of one or more new lesions is assessed as progression.

A lesion identified at a follow up assessment in an anatomical location that was not scanned at baseline is considered a new lesion and will indicate disease progression.

The finding of a new lesion should be unequivocal: i.e. not attributable to differences in scanning technique, change in imaging modality or findings thought to represent something other than tumor.

New lesions will be identified via a Yes/No tick box. The absence and presence of new lesions at each visit should be listed alongside the TL and NTL visit responses.

A new lesion indicates progression, so the overall visit response will be PD irrespective of the TL and NTL response.

If the question ‘Any new lesions since baseline’ has not been answered with Yes or No and the new lesion details are blank this is not evidence that no new lesions are present but should not overtly affect the derivation.

Symptomatic progression is not a descriptor for progression of NTLs: it is a reason for stopping study therapy and will not be included in any assessment of NTLs.

Patients with ‘symptomatic progression’ requiring discontinuation of treatment without objective evidence of disease progression at that time should continue to undergo tumor assessments where possible until objective disease progression is observed.

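### After a complete response, the SAP's Step 4 default can code a visit with one target lesion unmeasured and another regrown short of progression as CR, while the same visit without regrowth is NE

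*SAP*

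**What the plan says.** SAP 3.1.1.1, under the rules for TL responses after a CR, allows three categories: "A CR can only be followed by CR, PD or NE". The four steps are stated as mandatory at every later visit.

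- **First step:** CR, when every lesion still meets CR.
- **Second step:** the condition is "If some lesion measurements are missing but all other lesions meet the CR criteria". The visit is then NE, even where the sum of diameters would reach PD.
- **Third step:** PD, when at least one lesion has lost CR status and the sum reaches the PD threshold.
- **Fourth step:** for whatever is left, where "a response can still not be determined the response will be set to remain as CR".

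Step 4 makes no exception for unmeasured lesions.

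Other SAP text bears on this:

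- Section 3.1.1 assigns NE to an assessment that cannot be evaluated, unless there is evidence of progression.
- Table 6 describes NE as "Only relevant if any of the TLs were not assessed or NE or had a lesion intervention at this visit", and puts PD at a rise of at least 20% and at least 5 mm over the smallest previous sum.
- The Scaling paragraph says "CR will not be allowed as a TL response for visits where there is missing data", but its heading limits it to irradiated lesions and lesion intervention.
- The paragraph on change of assessment method says a TL response may still be evaluable if no more than one third of TL measurements are missing.

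**The concern.** Step 2 shows that the authors did not want a visit with an unmeasured lesion to count as a continuing CR, even when every measured lesion is still gone. Its wording covers only that situation. If a measured lesion has come back, Step 2 no longer applies. If the regrowth is too small for PD, Step 3 does not apply either, and the visit falls through to CR. This conflicts with the evident purpose of Step 2 and with the NE rule in Section 3.1.1.

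Table 8 (SAP 3.1.1.3) carries a TL CR to an overall CR, or to PR if non-target disease persists or is not evaluable. SAP 3.2.1 lets a scan at least 4 weeks later confirm a response, so the miscoded visit can turn an unconfirmed response into a confirmed one in the primary ORR. SAP Section 5 uses the same derivations for the Stage 1 review. The visit also counts as evaluable, so it can move a PFS or DoR censoring date later if no evaluable assessment, progression or death follows.

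**Working it through.** **The design that the ORR feeds.** The post-CR rule states no figure of its own, so I first reproduced the Simon design in SAP 1.3: n1 = 11, n = 26, continue at 2 or more responses, reject at 5 or more, null ORR 10%, alternative 30%. With b(n, x, p) the binomial probability,

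P(reject) = Σ over x = 2 to 11 of b(11, x, p) × P(Bin(15, p) ≥ 5 − x).

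This gives 0.0865 at p = 0.10 and 0.8516 at p = 0.30, within the stated 0.1 and 85%.

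**Step logic.** Steps 1 to 4 were applied literally with one TL unmeasured. Two assumptions are needed because the SAP is silent outside intervention. An unmeasured lesion adds nothing to the current sum in Step 3, while the nadir sum still includes it. Any rise from a nadir of 0 is taken to satisfy the 20% condition. PD then requires current sum − nadir sum ≥ 5 mm, and the 20% condition is also met in each case below.

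| Case | Nadir sum | PD when the measured TL reaches | NE (Step 2) | CR (Step 4) |
|---|---|---|---|---|
| A: two non-nodal TLs, 0 + 0 mm | 0 | 0 + 5 = 5 mm | 0 mm | above 0, below 5 mm |
| B: two nodes, 8 + 8 mm | 16 | 16 + 5 = 21 mm | below 10 mm | 10 to below 21 mm |
| C: missing node 9 mm, non-nodal TL 0 mm | 9 | 9 + 5 = 14 mm | 0 mm | above 0, below 14 mm |

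In every case the category runs NE, CR, PD as the measured lesion grows.

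Cases B and C are wider because nodes below 10 mm keep a size that counts in the sum. When such a node is missing, the current sum falls and can hide progression. Had the node been measured at its nadir size, PD would begin in B at 21 − 8 = 13 mm and in C at 14 − 9 = 5 mm.

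In case A, a lesion flagged as too small to measure is entered as 5 mm, which is PD from a nadir of 0. Case A therefore needs a smaller value that the radiologist has recorded as reliable.

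**What one responder can change, at a true ORR of 10%.**

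- Exactly 1 of 11 in Stage 1: 11 × 0.1 × 0.9^10 = 0.384.
- Past Stage 1 with exactly 4 of 26: Σ over x = 2 to 4 of b(11, x, 0.1) × b(15, 4 − x, 0.1) = 0.0569 + 0.0244 + 0.0033 ≈ 0.084 (0.0845 unrounded).

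These are the chances of standing where one extra responder flips the decision. They are not the chance that the rule supplies one.

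**Assumed range only.** If the rule added 1, 2 or 3 percentage points of false response to a true 10%, P(reject) would be 0.118, 0.153 or 0.193 instead of 0.087. The documents give no basis for any of these rates.

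**The case against.** The strongest reply is that the trigger is very narrow. It needs a first response that is a TL CR, then a visit with both an unmeasured TL and sub-PD regrowth, and no other confirming scan. If the first response was a PR and the CR came on a later scan, SAP 3.2.1 already counts it as confirmed. An NE visit does not rule out confirmation on a later scan, although the consecutive-assessment wording for BoR in SAP 3.2.5 might. Non-target progression or a new lesion still gives PD. CRs may be scarce: in the paediatric pembrolizumab study described in Protocol 2.2.1, the 6.1% response rate came from four PRs. Expansion decisions are also made by consensus of the Data Review Committee (Protocol 9.6.1). All of this stands and limits the size.

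A second reply is that the SAP does not treat every missing TL as NE, as the change-of-method paragraph shows. That is correct in general. After a CR, however, Step 2 already gives NE for a partly measured visit whose other lesions meet CR, with no one-third allowance. Giving CR when those lesions look worse is not explained by that paragraph.

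Three stronger readings are not supported:

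- A reader might infer that Step 4 breaks a general ban on CR with missing data. The sentence in question sits under a heading limited to intervention, and it allows PR and SD, which cannot follow a CR.
- A reader might infer that Table 6 makes any unassessed TL NE. It states when NE can be relevant, not that NE must follow.
- A reader might infer that any regrowth below 5 mm with a missing TL triggers the default. A node going from 6 to 9 mm still meets CR, so Step 2 gives NE; for nodes the window can also extend well above 5 mm.

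**Conclusion.** The point holds as a literal defect in a mandatory rule: after a CR, a visit with incomplete measurement and sub-PD regrowth gets a better category than the same visit without regrowth. It concerns TLs unmeasured for reasons other than intervention; intervened lesions have their own rules.

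The size is small and cannot be estimated. A reader might infer that each such visit adds a whole responder, 1/26 = 3.8 percentage points of ORR. That is so only when the CR is not otherwise confirmed and there is no non-target progression or new lesion. Nor do the documents support a claim that the type I error is inflated by any particular amount. It is still worth correcting, because one responder can decide at 2/11 or 5/26 and the conflict would otherwise be left to programming judgement in an open-label study.

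The conclusion rests on the two Step 3 assumptions stated in the working. Protocol Appendix E was not available to check whether it settles the matter. Step 4 also returns CR for sub-PD regrowth when all TLs are measured. That follows from allowing only CR, PD or NE after a CR, and is outside this point.

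**What to change.** In SAP 3.1.1.1, under the post-CR rules:

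1. Restrict Step 4 to visits at which all TLs were measured.
2. Add that if any TL is unmeasured and Step 3 does not give PD, the TL response is NE. Step 2 stays as it is.
3. For Step 3 at such visits, compare the measured lesions with the nadir sum of those same lesions, so that a missing node does not mask PD. PD then begins at 5 mm in case A, 8 + 5 = 13 mm in case B and 5 mm in case C, the same thresholds as if the missing lesion had been measured unchanged. The scaling ratio itself cannot be used in cases A and C, because its divisor, the nadir sum of the measured lesions, is 0.
4. State how these rules fit with the Scaling paragraph (which continues to govern intervened lesions) and with the one-third allowance after a change of method.

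The cost is a few lines of SAP text and a small programming change. A few visits may become NE or PD instead of CR. The Simon cut-offs and error rates do not change.
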